1.7.2 Secondary Hypotheses

- Administration of MEDI0382 once daily titrated up to a dose level of 300 µg across 49 days will have an acceptable safety profile and be well tolerated in overweight and obese subjects with T2DM
- Administration of MEDI0382 once daily titrated up to a dose level of 300 µg from 50 µg will have a predictable PK profile
- Administration of MEDI0382 once daily at a dose level of 50 µg will result in superior blood glucose control versus placebo after 7 days of treatment in overweight and obese subjects with T2DM

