3.2.3.2 Secondary Endpoints

Additional Measures of Glucose Lowering and Weight Loss

In order to better characterise the glucose-lowering efficacy of MEDI0382 up to 300 µg across 49 days of dosing, additional markers of glucose control including HbA1c and fasting glucose level will be measured, alongside exploratory measures of glucose control generated by CGM. Absolute change in weight will also be measured and the proportion of subjects achieving clinically significant weight loss (> 5% of body weight) will be recorded.

In evaluating the 50 µg dose of MEDI0382, this study will determine if repeat administration of 50 µg is more effective than placebo with respect to glucose lowering at 7 days through measurement of glucose AUC during a standardised MMTT. Results from the prior multiple-ascending-dose study (Study D5670C00002) of MEDI0382 on glucose AUC reduction have shown a reduction of 41.8% after 7 days at 100 µg, 36.7% after 11 days at 150 µg following up-titration from 100 µg, and 39.6% after 15 days at 200 µg following up-titration from 100 µg and 150 µg. Results from this previous study will be used as a benchmark to further evaluate the results.

Safety and Tolerability

In prior studies (Study D5670C00002), 300 µg of MEDI0382 has been administered to 23 obese and overweight subjects with T2DM for 7 days after 2 up-titration steps, and was shown to have an acceptable tolerability and safety profile over this period of dosing. During treatment, there was no significant increase in systolic or diastolic BP, but a significant increase in heart rate of 6.6 beats per minute (90% CI 4.1, 9.1) was recorded after 7 days of dosing (Cohorts 5 and 6 pooled data; n = 19). In the cohorts that received MEDI0382 up-titrated to 300 µg, nausea and vomiting were observed in a maximum of 41.7% (Cohort 6) and 27.3% (Cohort 5) of subjects, respectively. Safety and tolerability with greater exposure at the 300 µg dose level will be measured with safety laboratory tests, ABPM recording of heart rate and BP and other vital signs, and recording of AEs.

Pharmacokinetic Profile and Immunogenicity

Plasma concentrations of MEDI0382 at 50 and 300 µg will be used to evaluate the PK profile (C_{max} , time to maximum concentration [T_{max}], AUC_{tau} , and $C_{min}[R_0]$ [accumulation ratio]). In addition, C_{trough} at other dose levels will be evaluated to establish steady state achievement.

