 - o Day 1; vital signs to be taken; predose (-15 min), 15, 30, and 60 minutes (\pm 5 min) and 2 hours (\pm 10 min) postdose

- o Day 7, 15; 23 no specific time point
 - o Day 22, 29, 36, and 43; vital signs to be taken prior to fitting ABPM device
 - o Day 49: vital signs to be taken prior to fitting the ABPM device; postural (standing and supine) blood pressures should be performed at this time.
- f Subjects will be fitted with the ABPM device while at the clinical unit, which may involve practice inflations. The ABPM device should be applied on the opposite arm to the arm where the CGM device is applied. The subject will then wear the monitor/cuff for approximately 24 hours (including overnight at home) and will remove the device at home at the end of the 24-hour period. Subjects will return the device to the clinic.
- g A single digital ECG recording should be performed predose after the subject has rested for 10 minutes in the supine position on Day 1, 7, 22, and 49. No specific time point for other visits.
- h Body weight should be measured in the morning prior to breakfast (predose on Day 1); the subject should take off their shoes and remove bulky clothing. Calibrated scales should be used.
- i Randomisation may occur any time from Day -1 to Day 1 predosing.
- j Subjects are required to fast overnight on the night of Day -2, -1, 6, 21, 48, and 49. Refer to footnote (s) for additional fasting requirements on Day -2 and Day 49 during the day.
- k Subjects are required to dose at the clinic on Day 1 – 7 as dilution of dose is required by site staff. Subjects are also required to dose at the clinic on study day visits when predose assessments are required. See Section 4.5.1.3 for further information.
- l On Day 7, the subject will receive a final 50-µg dose, and should be provided with 7 days of IP supply to dose at the 100-µg dose level and advised to commence this dose level on Day 8 while they are at home. On Day 15, subjects will be given a 200-µg dose during their study visit, and should be provided with 6 days IP supply for dosing at the 200-µg dose level while at home. Subjects should be given the first 300-µg dose on Day 22 and continue this dose level for the remainder of the study.

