3 STATISTICAL METHODS

3.1 General Considerations

Data will be presented in data listings sorted by cohort and treatment, subject number and date collected, where appropriate. Tabular summaries will be presented by cohort and treatment group. Categorical data will be summarized by the number and percentage of subjects within each category. In general, continuous variables will be summarized by descriptive statistics including mean, standard deviation, median, minimum, and maximum.

The last observation carried forward (LOCF) will be used in efficacy and pharmacodynamics (PD) endpoints analyses unless otherwise specified. Baseline values will be defined as the last valid assessment prior to the first administration of study treatment unless otherwise specified.

All statistical tests will be 2-sided at an alpha = 0.1 significance level unless stated otherwise. There will be no adjustment for multiplicity.

Data analyses will be performed using SAS[®] version 9.3 or higher (SAS Institute Inc., Cary, NC).

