3.6.5 Vital Signs

Vital signs including pulse rate (beats/min), systolic and diastolic blood pressure (mmHg), temperature ($^{\circ}$ C), weight (kg), and respiratory rate (breaths/min), as well as the change from baseline for each of those parameters will be descriptively summarized by treatment group at each of the specified time points in the protocol.

The 24-hour average ambulatory blood pressure monitoring (ABPM) pulse rate (beats/min) and systolic and diastolic blood pressure (mm Hg) from the ABPM will be summarized by treatment group at each visit (Days -2, 22, 29, 36, 43, and 49) performed. The change from baseline (Day -2) for the 24-hour average pulse rate and systolic and diastolic blood pressure at each post-baseline visit will be analyzed with an ANCOVA with an effect for treatment and the baseline value as the covariate. The above summary and analyses will also be conducted for PR, SBP and DBP during asleep and awake periods.

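### The ambulatory heart rate and blood pressure analysis has 45 visit-wise tests but no lead estimate or committed confidence interval; one pooled 300 µg contrast per variable would resolve modest effects better

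*SAP*

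**What the plan says.** Protocol Table 2.2-1 lists 24-hour heart rate and blood pressure first among the measures for the secondary safety objective. The related hypothesis in Protocol 1.7.2 is that titration to 300 µg "will have an acceptable safety profile and be well tolerated in overweight and obese subjects with T2DM".

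SAP 3.6.5 takes ambulatory blood pressure monitoring (ABPM) on Day -2 as baseline and on Days 22, 29, 36, 43 and 49. Change in 24-hour average pulse rate and in "systolic and diastolic blood pressure at each post-baseline visit will be analyzed with an ANCOVA with an effect for treatment", with baseline as covariate. It then adds: "The above summary and analyses will also be conducted for PR, SBP and DBP during asleep and awake periods". Protocol 4.8.4.1 likewise specifies an ANCOVA on 24-hour means at different time points.

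The test level comes from SAP 3.1: "All statistical tests will be 2-sided at an alpha = 0.1 significance level unless stated otherwise". The same section says "There will be no adjustment for multiplicity". The 0.05 overrides appear only in the primary and secondary efficacy sections (SAP 3.4.1.2 and 3.4.2.2), so 0.10 governs ABPM.

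On dose, a footnote to Protocol Table 4.2.2-1 reads: "Subjects should be given the first 300-µg dose on Day 22 and continue this dose level for the remainder of the study". Protocol 3.2.1 puts steady state at 4 to 7 days.

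For ABPM, neither document names a lead visit or period, a confidence interval, a difference of concern or a power figure.

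**The concern.** Four of the five ABPM visits (Days 29, 36, 43 and 49) fall at least 7 days after the first 300 µg dose, so they repeatedly measure the effect of one dose at steady state. The plan tests them one at a time in 26 v 13 subjects and never combines them. The report could then contain 45 p-values with no prior statement of which one answers the safety question. A single-visit p > 0.10 says little about a modest rise, and an isolated p < 0.10 is quite likely by chance.

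The likely misreading is that non-significance means no effect. Protocol 3.2.3.2 describes earlier 300 µg data this way for blood pressure ("During treatment, there was no significant increase in systolic or diastolic BP"), next to a statement that safety was acceptable. In the same sentence it gives heart rate as an estimate with a 90% CI, which is the more useful form.

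**Working it through.** **Inputs.** Cohort 1 has 26 v 13 subjects (SAP 2.4); Cohort 2 has no ABPM (Protocol 3.1.1). Alpha is two-sided 0.10. The prior heart-rate rise at 300 µg is 6.6 bpm, 90% CI 4.1 to 9.1, n = 19 (Protocol 3.2.3.2). The documents give no SD for blood pressure and no between-visit correlation, so blood pressure results are in units of the baseline-adjusted residual SD and correlations are assumed.

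**Check of the method on the plan's own figures.** A two-sample noncentral t with 37 df at two-sided 0.05 gives 98.0% for a 28% glucose AUC difference at SD 20% (plan: 97%) and 85.0% for a 2.3% weight difference at SD 2.2% (plan: 85%). The method agrees to within about a point.

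**Number of tests.** 3 variables × 3 periods × 5 visits = 45; the 24-hour means alone give 3 × 5 = 15. Protocol 3.1.1 also has a final follow-up ABPM that is not in the SAP visit list; analysing it too would make 54.

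**One visit, in SD units.** With 36 df, t(0.95) = 1.688.
- Half-width of the 90% CI = 1.688 × √(1/26 + 1/13) = 1.688 × 0.340 = 0.573 SD.
- Noncentrality for 0.5 SD = 0.5 × √(26 × 13/39) = 0.5 × 2.944 = 1.472, giving power 42%.

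**One visit, heart rate.** If the prior interval is a one-sample t interval, SD = (2.5/1.734) × √19 = 6.3 bpm.
- Power is 92% for 6.6 bpm, 59% for 4.1 bpm and about 40% for 3 bpm. For 6.6 bpm it is 98.5% at SD 5, 77% at SD 8 and 60% at SD 10.
- A result at exactly p = 0.10 has estimate 0.573 × 6.3 = 3.6 bpm and 90% CI 0 to 7.2 bpm, which still contains 6.6 bpm.

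**Chance signals with no effect.** Expected p < 0.10 in the harm direction: 45 × 0.05 = 2.25. The tests are strongly dependent, so the chance of at least one was simulated with 26 v 13 subjects under two assumed correlation sets:

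| | Stronger | Weaker |
|---|---|---|
| Between visits | 0.8 | 0.4 |
| Heart rate with BP | 0.3 | 0.1 |
| SBP with DBP | 0.8 | 0.7 |
| 24-hour with awake | 0.95 | 0.93 |
| 24-hour with asleep | 0.85 | 0.75 |
| Awake with asleep | 0.7 | 0.5 |
| At least one harm-direction p < 0.10, 45 tests | 37% | 60% |
| Same, 15 24-hour tests | 25% | 40% |

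Counting both directions over all 45 tests gives about 68% to 91%, but that treats a fall in blood pressure as a false harm signal.

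**Average over Days 29, 36, 43 and 49.** The SD factor is √(ρ + (1 − ρ)/4), with ρ the between-visit correlation. Half-width = 0.573 × factor; noncentrality = 1.472/factor.

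| ρ | Factor | Half-width (SD) | Power for 0.5 SD |
|---|---|---|---|
| 0.8 | 0.922 | 0.529 | 47% |
| 0.6 | 0.837 | 0.480 | 53% |
| 0.3 | 0.689 | 0.395 | 67% |

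These assume complete data.

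**The case against.** **Exploratory phase 2a safety data are normally tested without adjustment.** This stands. Bonferroni over 45 tests (0.10/45 = 0.0022 each) would cut single-visit power for 6.6 bpm from 92% to 43%, which would hide harm. Neither the lack of adjustment nor the lack of a margin would justify a change on its own.

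**No decision depends on these p-values.** This also stands. A reader might infer that the plan takes p > 0.10 as proof of safety, but the objective is to characterise safety and no rule links an ABPM p-value to a conclusion. The sentence in Protocol 3.2.3.2 shows how such a result may be described, not a planned criterion.

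**The 24-hour mean already leads.** Partly true: the protocol's endpoint and analysis name only 24-hour values, and the SAP adds awake and asleep. Fifteen results still remain, with no lead visit.

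**An ANCOVA yields an interval anyway.** It can, and the separate programming plan may specify one. SAP 3.6.5 does not commit to it or say which interval to read.

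**Visit-wise analysis shows onset and time course, and an average dilutes a brief rise.** This stands. A 1-SD rise at one visit has 89% power there. In the four-visit average it becomes 0.25 SD, with power of about 20-28% for ρ from 0.8 to 0.3. The visit-wise results must therefore be kept.

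**Conclusion.** The point holds as a modest, inexpensive improvement, graded CONSIDER. The plan leaves precision unused on a named secondary safety measure and does not say in advance which ABPM estimate to read. The gain depends on an unknown correlation: small at 0.8 (power 42% to 47%), material at 0.3 (42% to 67%). Even then, 26 v 13 limits what can be excluded.

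Three stronger readings are tempting but not supported:
- That ABPM is the only safety measure formally tested. Protocol 2.3 lists gastrointestinal event percentages as exploratory safety endpoints, and Protocol 4.8.3.3 assigns logistic regression to exploratory proportions. Part of SAP 3.6.1 is also redacted.
- That no ABPM result could separate harm from no harm. At an SD of 6.3 bpm, a consistent rise near 6.6 bpm would be seen. The weakness concerns smaller heart-rate effects and blood pressure.
- That all five visits measure the same thing. Day 22 is the first 300 µg day, before the 4 to 7 days the protocol gives for steady state.

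The 6.3 bpm SD is itself an assumption: the protocol does not say whether the 6.6 bpm was against baseline or placebo, or clinic or ambulatory.

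**What to change.** In SAP 3.6.5, before unblinding:

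1. For 24-hour mean pulse rate, SBP and DBP, add one repeated-measures model per variable with treatment, visit, treatment-by-visit and baseline.
2. Name as the lead ABPM estimate the MEDI0382 minus placebo difference averaged over Days 29, 36, 43 and 49, with its two-sided 90% CI.
3. State that the safety reading is the upper limit of that interval (a one-sided 95% bound), and that p > 0.10 will not be described as no increase.
4. Keep the Day 22 result and all the visit-wise ANCOVAs, including awake and asleep, as supportive estimates with 90% CIs to show onset and time course.

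The cost is SAP wording and three extra models, with no new visits or subjects. The protocol's ANCOVAs are retained, so the models are an addition to Protocol 4.8.4.1; their lead status should be recorded as such. The remaining downside is dilution of a rise confined to one visit, which item 4 would show.

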3.2 Study Design and Dose Rationale

3.2.1 Dose Rationale

PK information collected in previous single and multiple dose clinical studies (Studies D5670C00001 and D5670C00002) suggest that MEDI0382 has a linear profile in the dose range 5 to 300 μ g with a half-life of approximately 8 to 13 hours, which allows minimal accumulation after repeat daily administration and achievement of steady state between 4 and 7 days. Moreover, the absorption profile in the low-dose range tested suggests that doses lower than 100 μ g may have a different bioavailability to doses greater than 100 μ g.

Based on PK/pharmacodynamics (PD) modelling conducted using available clinical data and from a literature review of GLP-1 and glucagon modulators, the maximal clinically efficacious dose for glucose control of MEDI0382 was predicted to be in the range of 200 to 300 μ g/day; in addition early clinical data from a prior single-ascending-dose study (Study D5670C00001) identified potentially efficacious doses in a range lower than 100 μ g. However, there is no information available on efficacy with repeat dosing at dose levels below 100 μ g. The initial dose for Cohorts 1 and 2 of this study is therefore proposed to be 50 μ g and the maximum dose to be administered in this study will not exceed 300 μ g/day. As

described above, the principle of dose up-titration to improve tolerability with higher doses is well established with short-acting GLP-1 analogues ([Victoza, 2014](#)).

The study is designed to provide efficacy information on glucose control and weight loss at 300 µg administered daily for 28 days to allow comparison with previous clinical data collected at 200 µg at a similar administration duration. It will also explore a prolonged dose titration schedule for repeated doses of MEDI0382 to characterise the safety/tolerability profile and PK/PD profile of MEDI0382 at a relevant pharmacological range to facilitate rational design of future studies. Moreover, it is designed to establish the efficacy of repeated dosing of 50 µg MEDI0382 on glucose control.

[REDACTED]

[REDACTED]

[REDACTED]

[REDACTED]

[REDACTED]

[REDACTED]	[REDACTED]	[REDACTED]	[REDACTED]	[REDACTED]
[REDACTED]	[REDACTED]	[REDACTED]	[REDACTED]	[REDACTED]
[REDACTED]	[REDACTED]	[REDACTED]	[REDACTED]	[REDACTED]
[REDACTED]	[REDACTED]	[REDACTED]	[REDACTED]	[REDACTED]
[REDACTED]	[REDACTED]	[REDACTED]	[REDACTED]	[REDACTED]
[REDACTED]	[REDACTED]	[REDACTED]	[REDACTED]	[REDACTED]

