4.1.6 Discontinuation of Investigational Product

An individual subject will not receive any further investigational product if any of the following occur in the subject in question:

- Withdrawal of consent from further treatment with investigational product or lost to follow-up
- An AE that, in the opinion of the investigator or the sponsor, contraindicates further dosing
- Subject is determined to have met one or more of the exclusion criteria or failed to meet all of the inclusion criteria for study participation at study entry and continuing investigational product, in the decision of the investigator, might constitute a safety risk
- Subject noncompliance that, in the opinion of the investigator or sponsor, warrants withdrawal (eg, refusal to adhere to scheduled visits).
- Pregnancy in a female subject

Subjects who are permanently discontinued from receiving investigational product will be followed for protocol-specified assessments including follow-up of any AEs unless consent is withdrawn specifically from further study participation (Section 4.1.5), the subject is lost to follow-up, the subject starts alternative treatment, or the subject is enrolled in another clinical study.

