4.8.4.1 Analysis of Clinical Laboratory Parameters

Other safety data, such as vital signs, clinical laboratory data, ECG, and physical examination findings, will be descriptively summarised at each time point by treatment. Mean ambulatory BP and heart rate measurements recorded over 24 hours at different time points will be analysed using an ANCOVA model, adjusting for treatment and measurement at baseline. ADA incidence rate and titre will be tabulated for each treatment.

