3.2 Analysis Populations

The analysis populations are defined in Table 3.2-1.

Table 3.2-1 Analysis Populations

Population	Description
Intent-to-treat (ITT) population	Subjects who receive any study investigational product will be included in the ITT population and subjects will be analyzed according to their randomized treatment group.
As-treated population	Subjects who receive any study investigational product will be included in the as-treated population will be analyzed according to the treatment they received.
PK population	The PK population includes all subjects who received at least one dose of MEDI0382 and had at least one post-baseline MEDI0382 PK sample with a value above the lower limit of quantitation.
PD population	The PD population includes all subjects who received at least one dose of investigational product and had at least one post-baseline PD sample or PD evaluation [REDACTED]

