3.6 Safety Analyses

The analyses will be based on the As-treated population. All safety summaries will be presented by treatment group for each cohort, unless otherwise specified.

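### The ambulatory heart-rate and blood-pressure analysis has no on-drug counterpart, so its MEDI0382 contrast at Days 22 to 49 would be diluted if subjects who stop product are still recorded

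*SAP*

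**What the plan says.** Ambulatory blood pressure monitoring (ABPM) is done in Cohort 1 only.

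- **Model.** SAP 3.6.5 summarises 24-hour averages "at each visit (Days -2, 22, 29, 36, 43, and 49) performed". The change from baseline "at each post-baseline visit will be analyzed with an ANCOVA with an effect for treatment and the baseline value as the covariate". Protocol 4.8.4.1 gives the same model, with terms for treatment and the baseline value: "Mean ambulatory BP and heart rate measurements recorded over 24 hours at different time points will be analysed using an ANCOVA model". Neither text mentions dosing status.
- **Analysis set.** SAP 3.6: "The analyses will be based on the As-treated population". SAP 3.2 defines it: "Subjects who receive any study investigational product will be included in the as-treated population will be analyzed according to the treatment they received". It has no time-on-drug limit.
- **Follow-up after stopping product.** Protocol 4.1.6: "Subjects who are permanently discontinued from receiving investigational product will be followed for protocol-specified assessments". The exceptions listed there are withdrawal of consent, loss to follow-up, starting alternative treatment, and joining another clinical study.
- **Missing data.** SAP 3.1 applies last observation carried forward to efficacy and pharmacodynamic endpoints only. The data at issue here are therefore real recordings, not carried-forward values.

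**The concern.** Twenty-four-hour heart rate and blood pressure are named among the secondary safety measures in Protocol 2.2. Protocol 3.2.3.2 says that ambulatory recording will help to measure safety with longer exposure to 300 µg, after an earlier study found a rise in heart rate at that dose. A reader will therefore take the Day 22 to 49 contrasts as the evidence on this question.

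A subject who stopped during titration never received 300 µg, yet counts as MEDI0382 at every ambulatory visit attended. If the effect fades off drug, these recordings pull the active mean towards placebo. For efficacy such dilution is cautious. For a safety effect it is falsely reassuring. Protocol 3.2.3.3 reports nausea in 52% and vomiting in 32% of subjects dosed up to 200 µg in the earlier study, so tolerability stops in the active arm are plausible, although no rate is given.

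**Working it through.** The plan states no power or precision for the ambulatory analysis, so there is no figure of its own to reproduce. The check has four steps.

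**1. Can off-drug recordings enter the model?** Taken together, SAP 3.2, 3.6 and 3.6.5 include every recording from anyone ever dosed. Protocol 4.1.6 allows recordings after the last dose, apart from its exceptions. No section of either document excludes, flags or separately analyses them. So they can enter.

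**2. Which dose period do the visits cover?** Protocol 3.1.2 gives Cohort 1 three titration steps of 7 days, and 3 × 7 = 21. The 300 µg period therefore starts on Day 22 and runs to Day 49. All five post-baseline visits in SAP 3.6.5 (Days 22, 29, 36, 43 and 49) fall within it.

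**3. How much drug is left after stopping?** Protocol 3.2.1 gives a "half-life of approximately 8 to 13 hours". The share remaining after t hours with half-life h is 2^(−t/h).

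| Time since last dose | h = 8 | h = 13 |
|---|---|---|
| 24 h | 12.5% | 27.8% |
| 48 h | 1.6% | 7.7% |
| 72 h | 0.2% | 2.2% |
| 168 h | below 0.001% | 0.013% |

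One week after stopping, a subject is effectively unexposed.

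**4. How large is the dilution?** Let D be the on-drug difference from placebo, and let k active subjects be off drug but recorded at a visit. Assume no effect remains off drug and the placebo mean is unchanged. With n active subjects recorded, the expected contrast is D × (1 − k/n), a proportional loss of k/n. The documents do not give k, so the range below is an assumption. Protocol 4.1.1 plans 26 active subjects. Protocol 4.6.1.1 aims for up to 26 to complete dosing, so the third column treats those who stop as additional to 26 completers.

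| k (assumed) | Loss, 26 recorded in all | Loss, k in addition to 26 |
|---|---|---|
| 0 | 0% | 0% |
| 1 | 1/26 = 3.8% | 1/27 = 3.7% |
| 2 | 2/26 = 7.7% | 2/28 = 7.1% |
| 4 | 4/26 = 15.4% | 4/30 = 13.3% |
| 6 | 6/26 = 23.1% | 6/32 = 18.8% |

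If a share r of the effect persists off drug, each loss is multiplied by (1 − r).

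For scale only, Protocol 3.2.3.2 reports an earlier rise of 6.6 beats per minute after 7 days of dosing (90% CI 4.1 to 9.1, n = 19). If D were 6.6, each off-drug subject among 26 would remove 6.6/26 = 0.25 beats per minute, and four would leave 6.6 × 22/26 = 5.58. The protocol does not say that this figure is placebo-adjusted or a 24-hour ambulatory mean.

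**The case against.** The strongest reply is that the all-recordings As-treated comparison is a legitimate estimate. The safety objective in Protocol 2.2 covers both dosing and follow-up, and SAP 3.6.5 compares treatment groups without calling the result a 300 µg effect. Its visit list also omits the final follow-up recording in Protocol Table 4.2.3-1, the one recording that is off drug by design. This stands: the planned analysis is not an error and should stay. What is missing is an on-drug estimate beside it.

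Second, there may be few or no off-drug recordings. The exceptions in Protocol 4.1.6 end follow-up for some subjects, and the early discontinuation visit in Protocol 4.2.3.1 has no ABPM. This also stands as a limit on size. It does not close the gap, because subjects can stop product and remain in the study, and the early discontinuation list is for those who leave the study or need an unscheduled visit.

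Third, disposition, doses received and discontinuations due to adverse events are already reported (SAP 3.3.1, 3.3.3 and 3.6.3). These indicate the overall share off drug but not how many ambulatory recordings at each visit were off drug. The statistical programming plan might add detail, but it is not among the documents.

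A reader might go further and infer that the on-drug set should become the main analysis. The documents do not support that. Restricting to subjects still dosing conditions on an event after randomisation. If those with the largest heart-rate rise or worst tolerability stop, the on-drug estimate is also pulled towards zero.

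**Conclusion.** The point holds conditionally. The ambulatory ANCOVA has no on-drug condition, and the protocol allows recordings after product is stopped. If such recordings occur and the effect is lost off drug, the active contrast at the 300 µg visits is diluted towards zero by about 3.8% per off-drug subject when 26 active subjects are recorded.

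That figure rests on three assumptions: 26 recorded subjects, no remaining effect, and an unchanged placebo mean. The second is inferred from plasma half-life, since the documents give no time course for reversal of heart rate or blood pressure.

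A reader might infer that the plan does understate the effect of 300 µg, or that a definite amount of power is lost. Neither is supported. No discontinuation rate is given, so the dilution is unknown and is zero if nobody stops product or if all who stop leave the study. No standard deviation is given for the 24-hour measures, and no decision rule is attached to this analysis. It is a cheap improvement worth making, not a flaw that invalidates the analysis.

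**What to change.** In SAP 3.6.5:

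1. Keep the all-recordings As-treated ANCOVA as written.
2. Pre-specify beside it the same ANCOVA at each visit, restricted to recordings started within a stated short window after the last dose of investigational product. Set the window's length before unblinding and justify it from the half-life. A window is better than requiring a dose on the day of fitting. The same-day rule would drop a subject who missed one morning dose and still has 12.5% to 27.8% of the previous day's dose on board, and would keep one who had just restarted after a gap.
3. Report the number of on-drug and off-drug recordings by arm and visit.
4. State that the two estimates are read together and neither replaces the other.

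The cost is a few lines of SAP text and one extra run of an existing model, with no new data collection. The downside is that the on-drug set is slightly smaller and selected on tolerability, which can also bias it towards zero.
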